4.3.2 Duplicate efficacy assessments

The assessments for laboratory parameters will be based only on central laboratory values. For laboratory efficacy parameters, if a patient has more than one measurement (scheduled or unscheduled) included within a relative day window, the assessment closest to the target day and time (the target time is always assumed to be 8:00 am) will be used. In case of ties between observations located on different sides of the target day and time, the later assessment will be used. In case of ties located on the same side of the target day and time (i.e. more than 1 value for the same day and time), the mean of the values will be used.

For non-laboratory efficacy parameters, if a patient has more than one measurement (scheduled or unscheduled) included within a relative day window, the assessment closest to the target day will be used. In case of ties between observations located on different sides of the target day, the later assessment will be used. In case of ties located on the same side of the target day (i.e., more than 1 value for the same day), the mean of the values will be used.

4.3.3 Visit assignment for safety variables

Below tables provide day windows for vital signs, safety lab parameters (clinical chemistry/hematology), and growth and development hormones.

Table 3.5 Visit Windows: Vital signs

Visit	Analysis Visit	Week	Period	Target Day	Day range
2	0	0	CAP	1	Baseline
3	1	4	CAP	29	2-42
4	2	8	CAP	57	43-70
5	3	12	CAP	85	71-105
6	4	18	CAP	127	106-147
7	5	24	CAP	minimum (last day of CAP or 169)	148 to last day of CAP
8	6	28	EP	maximum (last day of CAP+1 or 197)	last day of CAP +1 to 238
9	7	40	EP	281	239-322
10	8	52	EP	minimum (last day of EP or 365)	323 to last day of EP

CAP: Controlled assessment period. EP: Extension period.

Table 3.6 Visit Windows: Injection site reaction

Visit	Analysis Visit	Week	Period	Day range
3	1	4	CAP	1-42
4	2	8	CAP	43-70
5	3	12	CAP	71-105
6	4	18	CAP	106-147
7	5	24	CAP	Subjects not entering EP: 148 to last day of CAP
				Subjects entering EP: 148 to last day of CAP -1
8	6	28	EP	Subjects not entering EP: last day of CAP +1 to 238
				Subjects entering EP: last day of CAP to 238
9	7	40	EP	239-322
10	8	52	EP	323 to last day of EP

CAP: Controlled assessment period. EP: Extension period.

Table 3.7 Visit Windows: Total testosterone, SHBG, Tanner Pubertal Stage

Visit	Analysis Visit	Week	Period	Target Day	Day range
2	0	0	CAP	1	Baseline
5	3	12	CAP	85	2-126
7	5	24	CAP	minimum (last day of CAP or 169)	127 to last day of CAP
9	7	40	EP	maximum (last day of CAP+1 or 281)	last day of CAP +1 to 322
10	8	52	EP	minimum (last day of EP or 365)	323- last day of EP

CAP: Controlled assessment period. EP: Extension period.

Table 3.8 Visit Windows: Laboratory (hematology, clinical chemistry, urinalysis), Growth and development hormones such as TSH, FSH etc., Bone specific Alkaline phosphatase and N-telopeptide.

Visit	Analysis Visit	Week	Period	Target Day	Day range
2	0	0	CAP	1	Baseline
5	3	12	CAP	85	71-126
7	5	24	CAP	minimum (last day of CAP or 169)	127 to last day of CAP
10	8	52	EP	minimum (last day of EP or 365)	last day of CAP +1 to last day of EP

CAP: Controlled assessment period. EP: Extension period.

Table 3.9 Visit Windows: calcitonin, pancreatic amylase, lipase, CEA

Visit	Analysis Visit	Week	Period	Target Day	Day range
2	0	0	CAP	1	Baseline
5	3	12	CAP	minimum (last day of CAP or 85)	71 to last day of CAP
10	8	52	EP	minimum (last day of EP or 365)	last day of CAP +1 to last day of EP

CAP: Controlled assessment period. EP: Extension period.

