6.4.10 Injection site reaction assessment

Small, asymptomatic, SC nodule formation at the injection site is an expected event associated with sustained release delivery systems.

The assessment of injection site reactions will be performed by the Investigator or subinvestigator according to the schedules presented in the Study Plan (Table 1) and Section 6.2.

Assessments should be done by interviewing the patient and/or the patient's parent(s) or caregiver(s), and be performing physical assessment of the injection site. All relevant information regarding injection site reactions, including reaction type, location, severity, and action taken, should be reported by the Investigator in the Injection Site Reaction Module of the eCRF, including all injection site reactions that meet the criteria for an AE.

Classification of whether an injection site reaction is an AE or not an AE should be made based on the definition of an AE as described in Section 6.4.1. Determination of whether an injection site reaction AE should be classified as serious should be done based on the standard SAE definition as described in Section 6.4.2, as with all other AEs.

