3.6.5.2 Safety and concomitant medications

Adverse events, hypoglycemic events and concomitant medications on the date of first dose of open-label EQW (Week 24 visit) will be assigned to the extension period as this is considered a conservative approach. Other safety assessments at the Week 24 visit will be considered to have been carried out pre-dose and will therefore be assigned to the controlled assessment period. This is reflected in the definitions below.

Controlled assessment period:

- For patients who do not enter the extension period, the controlled assessment period will be defined as date of first dose of randomized study medication to date of last dose of randomized study medication + 7 days (or + 90 days after last dose of study medication for reporting of serious adverse events (SAEs) and other clinically significant or related AEs).
- For patients who go on to enter the extension period, the controlled assessment period for all safety parameters except AEs, hypoglycemic events and concomitant medications will be defined as date of first dose of randomized study medication to date of first dose of open-label EQW. For AEs, hypoglycemic events and concomitant medications, the controlled assessment period will be defined as date of first dose of randomized study medication to date of the first dose of open-label EQW – 1 day, in order for AEs, hypoglycemic events and medications recorded on the date of first dose of open-label EQW to be assigned to the extension period.

Extension period: For all safety parameters, except AEs, hypoglycemic events and concomitant medications, the extension period will be defined as date of first dose of open-

label EQW + 1 to date of last dose of open-label EQW + 7 days. For AEs, hypoglycemic events and concomitant medications, the extension period will be defined as date of first dose of open-label EQW to date of last dose of open-label EQW + 7 days (or + 90 days for SAEs and other clinically significant or related AEs). The extension period will only be defined for patients who enter the extension period and receive at least one dose of open-label EQW.

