Tables of key patient information for SAEs and AEs leading to discontinuation of study medication will be provided. Adverse events will be listed.

The number of AEs and number of SAEs will be summarized for the controlled assessment period and extension period.

The denominator for summaries will be the number of patients included in the analysis set by treatment group and total. Where the controlled assessment period and extension period are presented side-by-side in the same summary, the denominator for the controlled assessment period will be the number of patients in the Safety analysis set by treatment group and total; the denominator for the extension period will be the number of patients in the subset of Safety patients who received open-label EQW during the extension period by treatment group and total.

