4.2.4.2 Injection-site reactions

Proportions of patients reporting different injection site reactions at Visit 3 (Week 4) through Visit 10 (Week 52).

Injection-site reactions will be identified from the AE dataset using the higher-level term (HLT) “Injection site reactions”. Injection-site reactions reported on the INJECT eCRF will not be included in summaries as this eCRF was introduced part-way through the study and therefore does not provide a complete picture of the number of injection-site reactions. Data reported on the INJECT form will be listed only.

The number and percentage of patients reporting different injection site reactions, per the AE dataset, will be summarized by visit (see Section 4.3.3 for details on visit windows for injection site reactions). This will be provided separately for both the Safety analysis set during the controlled assessment period and for the subset of Safety patients who received open-label EQW during the extension period for the Treatment period. The injection site reactions will be additionally repeated by injection device type i.e. pre-filled syringe or dual-chamber pen. All patients randomized to the study on or after 12th August 2018 are dispensed dual chamber pen devices.

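### By-visit injection-site reaction percentages use windows of 21 to 84 days without adjusting for time at risk, so a constant rate shows an artificial step where placebo patients switch to EQW

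*SAP*

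**What the plan says.** SAP 4.2.4.2 takes reactions from AE records: "The number and percentage of patients reporting different injection site reactions, per the AE dataset, will be summarized by visit". The dedicated injection-site form was introduced part-way through the study, so its data are only listed. The summary is produced for the controlled period (CAP) in the Safety set. It is produced again over the whole treatment period for patients who received open-label EQW, and repeated by device type.

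Table 3.6 (SAP 4.3.3) sets the windows. At the switch, Week 24 is "Subjects entering EP: 148 to last day of CAP -1" and Week 28 is "Subjects entering EP: last day of CAP to 238"; Week 52 is "323 to last day of EP". A note in SAP 1.2 places the first open-label dose at the Week 24 visit.

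Section 4.2.4.2 gives no denominator by window and no exposure adjustment. The neighbouring AE section, 4.2.4.1, says: "The denominator for summaries will be the number of patients included in the analysis set by treatment group and total". The rescue summary in 4.2.3.5, by contrast, does define how many patients are counted at each visit.

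**The concern.** For a measurement, window width matters little: SAP 4.3.4.1 selects the one value closest to the target day. A reaction is an event. Table 3.6 has no target days and the count is of patients with any reaction in the window, so each extra day is another chance to be counted. The percentages are therefore comparable across visits only if the windows are of similar length, and they are not.

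The largest mismatch between adjacent windows is at the switch. The treatment-period table shows Week 24 beside Week 28 in the same patients, under the Placebo -> EQW label of SAP 4.1.1, and a reader will look there for the effect of starting EQW. In the EQW group, the same pattern could be read as reactions becoming more frequent with longer use.

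**Working it through.** The plan states no reaction rate and no window length, so there is no figure of its own to reproduce.

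**Window lengths.** Length = last day − first day + 1, from Table 3.6, for patients entering the extension. For safety variables other than AEs, hypoglycaemic events and concomitant medication, SAP 3.6.5.2 has CAP "defined as date of first dose of randomized study medication to date of first dose of open-label EQW". Taking that date as Day 169:

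| Visit | Days | Length |
|---|---|---|
| Week 4 | 1–42 | 42 |
| Week 8 | 43–70 | 28 |
| Week 12 | 71–105 | 35 |
| Week 18 | 106–147 | 42 |
| Week 24 | 148–168 | 21 |
| Week 28 | 169–238 | 70 |
| Week 40 | 239–322 | 84 |
| Week 52 | 323–365, or to 372 | 43 to 50 |

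The upper Week 52 figure takes the last dose on Day 365 plus the 7 days of SAP 3.6.5.2. The cut points are midpoints between target visit days, except at the switch. There the midpoint of Days 169 and 197 would give 183, but the cut is at the end of CAP, so Week 24 is shortened and Week 28 lengthened.

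**Ratio at the switch.** 70/21 = 3.33. With the Week 24 visit 2 days early it is 72/19 = 3.79; with it 2 days late, 68/23 = 2.96. Under the separate CAP definition for AEs in 3.6.5.2, which ends the day before the first open-label dose, it is 71/20 = 3.55, and the last pre-switch day falls into Week 28.

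**Effect on the percentages.** Assume placement by onset date and a constant rate. If a proportion p of patients react per 28 days, the expected percentage in d days is 1 − (1 − p)^(d/28). For p = 10%, Week 24 is 1 − 0.9^0.75 = 7.6% and Week 28 is 1 − 0.9^2.5 = 23.2%.

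| Assumed p per 28 days | Week 24 | Week 28 | Ratio |
|---|---|---|---|
| 1% | 0.8% | 2.5% | 3.30 |
| 5% | 3.8% | 12.0% | 3.19 |
| 10% | 7.6% | 23.2% | 3.05 |
| 20% | 15.4% | 42.8% | 2.77 |
| 30% | 23.5% | 59.0% | 2.51 |
| 50% | 40.5% | 82.3% | 2.03 |

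At p = 10%, a flat rate shows across the eight visits as 14.6, 10.0, 12.3, 14.6, 7.6, 23.2, 27.1 and 14.9% (Week 52 at 43 days).

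**Does a rate remove the step?** At p = 10% the constant rate is −ln(0.9)/4 = 0.0263 per week, or 2.63 per 100 patient-weeks in every window, if each patient's time stops at the first reaction in the window. Dividing by the full window instead gives 7.6/3 = 2.53 and 23.2/10 = 2.32: close, but slightly over-corrected. At p = 50% the over-correction is larger: 40.5/3 = 13.5 against 82.3/10 = 8.2.

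**Would visit-ended windows do instead?** Week 24 would be Days 128–168 (41 days) and Week 28 Days 169–197 (29 days). At an assumed 2% per week, 1 − exp(−0.02 × 41/7) = 11.1% and 1 − exp(−0.02 × 29/7) = 8.0%. The false rise becomes a false fall.

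**The case against.** The strongest answer is that the table contains its own control. The EQW group has the same windows, so under a constant rate it shows the same step, and the Placebo -> EQW column can be judged against it. The table is descriptive and carries no test. SAP 4.2.4.1 also presents AEs by preferred term and by study period, about 24 weeks against 28, which compares the time before and after the switch almost evenly. All of this stands, and it is why the point is minor.

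Three stronger readings are tempting but unsupported. A reader might infer that the fixed denominator causes the step. That rule is written in 4.2.4.1 and not repeated in 4.2.4.2. In any case, everyone in the treatment-period table entered the extension, so an at-risk count would be nearly the same at Weeks 24 and 28; window length drives the step. A reader might also say that the percentage always triples. The ratio is 3 or more only up to about 11.7% of patients per 28 days, and Protocol 6.4.10 calls nodules an expected event, so higher rates cannot be excluded. Finally, a reader might take the windows for a careless copy of the measurement windows. The documents do not show this: Table 3.6 starts at Day 1, drops target days and places switch-day events in the extension, in line with 3.6.5.2.

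**Conclusion.** The point holds as a minor defect of presentation. Percentages from windows of 21 to 84 days cannot be read as a time trend. At the switch, a constant rate would appear to rise about 2.8- to 3.3-fold for up to 20% of patients per 28 days, and about 2-fold at 50%. This rests on onset-date placement, which Table 3.6 does not state (Table 3.1 does state start date for rescue medication), on a first open-label dose on Day 169, and on assumed rates.

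A reader might infer that the table would manufacture a treatment effect of EQW. It would not: comparison of the two groups within a visit is unaffected. What is distorted is the trend within each group, including the before-and-after reading of Placebo -> EQW and of its repeat by device type.

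**What to change.** Keep the Table 3.6 windows and the protocol's proportions. In SAP 4.2.4.2:

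- Add, for each window, the number of patients with a reaction per 100 patient-weeks (or per 100 injections), counting only time on study medication in that window. Stop each patient's time at the first reaction in the window, so that a constant rate gives the same value throughout.
- Show the window lengths in a footnote.
- State that reactions are assigned by onset date, and which CAP definition in 3.6.5.2 governs Table 3.6.

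Do not redraw the windows: ending them on visits leaves them unequal (41 against 29 days at Weeks 24 and 28) and reverses the artefact. The cost is SAP wording, one more column and some reprogramming of this summary and its repeat by device type. No new data are needed.

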6.2.3.10 Visit 10 (Week 52) - End of Treatment or Early Termination

Prior to Visit 10 (Week 52) or Early Termination, patients will have fasted overnight (≥ 8 hours).

All patients will undergo the following procedures:

- Review of concomitant medication and AEs
- Physical examination will be performed
- Body weight, height, and vital signs will be measured
- Assessment of Tanner pubertal stage
- Injection site reaction assessment will be performed
- Urine will be collected for:
 - Pregnancy test (females only) (only for Visit 10 [Week 52])
 - Urinalysis
 - Urinary albumin creatinine ratio
 - N-telopeptide.
- Blood samples will be collected for:
 - Serum pregnancy test (β hCG) for all female patients (only for early termination visit)
 - Chemistry and hematology
 - HbA1c
 - Fasting plasma glucose
 - Fasting insulin
 - Calcitonin
 - Pancreatic amylase and lipase
 - Fasting lipids (TC, HDL-C, LDL-C, and TG)
 - TSH, FSH, LH, total testosterone, SHBG, estradiol, free T4, prolactin, cortisol, IGF-1, DHEAS, and bone specific alkaline phosphatase

- CEA
- Measurement of antibodies to exenatide
- Measurement of plasma exenatide.
- Bone age assessment by X-ray
- Patients will have a study medication compliance review
- Patients will be asked to return used/unused study medication.

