3.6.3 Early Termination visit

If a patient discontinues after randomization but prior to completion of the study treatment period, the patient will be invited to return as soon as possible to the study site for an early termination (ET) visit. Patients will be invited to return to the study site for an ET visit to collect HbA1c, fasting plasma glucose, body weight, and clinical safety laboratory measures. Patients who discontinue study medication prior to Visit 11 (Week 62/Study Termination) will also participate in the Extended Safety Follow-up Period, unless they have a height increase of less than 5 mm over a 6-month interval at study-site visits prior to discontinuation of study medication.

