4.2.4.4 Clinical laboratory

Continuous clinical laboratory parameters will be summarized in standardized international (SI) and US conventional units.

For quantitative measurements, observed values and changes from baseline to each post-baseline visit will be determined by visit windows described in Section 4.3.1 and 4.3.3.

All hematology, clinical chemistry, growth and development hormones and urinalysis results will be listed by treatment group, patient, and visit, including scheduled and unscheduled/repeat measurements. Laboratory assessments that are outside of normal ranges will be flagged.

Baseline values, the observed values at each visit to Week 52 and including the 10-week follow-up, as well as change from baseline values will be summarized for each of the quantitative laboratory assessments by treatment group. Additionally, listings by individual patients' data will be reported as appropriate.

Clinical laboratory results (chemistry, hematology, growth and development hormones and urinalysis) will be summarized using descriptive statistics for each visit. Shift from baseline to the minimum/maximum value during treatment will be presented for the controlled assessment period and extension period, separately, based on high/low/normal findings for clinical laboratory parameters if normal ranges are available (for quantitative measurements and categorical measurements). For the categorical Urine-Blood parameters, a shift table from baseline to every planned visit will be performed. For the categorical measurements Urine Glucose, Ketones and Urine Total Protein, results will be presented under the following categories: 0, trace, +1, +2, +3.

Number and percentage of laboratory results that are potentially clinically significant (see [Appendix B3](#)) will be summarized by analyte name and criteria for each treatment group.

Estimated glomerular filtration rate will be derived based on the Bedside Schwartz formula:

$$eGFR = 41.3 * (\text{Height in meters} / \text{Serum creatinine in mg/dL})$$

A table of observed and change from baseline in eGFR values will be provided. This will be provided both overall and by baseline eGFR, hyperfiltrating versus non-hyperfiltrating, where hyperfiltration is defined as an $eGFR \geq 125 \text{ ml/min/1.73m}^2$.

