4.3 Conventions

4.3.1 Visit assignments for efficacy variables

All visits scheduled during the 24-week controlled assessment and 28-week extension period should occur within ± 2 days of the scheduled date relative to Visit 2 (Week 0) per the CSP.

Patients do not always adhere strictly to the visit timing in the CSP. Therefore, the designation of visits during the treatment period will be based on the day of evaluation relative to the start of the controlled assessment period (day of study medication = Day 1) rather than the nominal visit recorded in the eCRF.

To assign a measurement to a Week t during the study, the first step is to select all measurements falling within the study period. Mutually exclusive relative day windows are used to determine the Week t measurement. These relative day windows are defined to provide derived visits that correspond to the post-baseline time points specified in the CSP. Some restrictions may exist on some laboratory assessments to be included in efficacy analyses. These restrictions will be reflected in the relative day ranges. Visit windows for efficacy variables are listed below.

Visit windows will not be used for Visit 11 (Week 62) and data will be presented per the visit label.

Table 3.1 Visit Windows: HbA1c, Body weight, BMI, Rescue medication (based on start date of medication) and blood pressure

Visit	Analysis Visit	Week	Period	Target Day	Day range
2	0	0	CAP	1	Baseline
3	1	4	CAP	29	2-42
4	2	8	CAP	57	43-70
5	3	12	CAP	85	71-105
6	4	18	CAP	127	106-147
7	5	24	CAP	minimum (last day of CAP or 169)	148 to last day of CAP

Visit	Analysis Visit	Week	Period	Target Day	Day range
8	6	28	EP	maximum (last day of CAP+1 or 197)	last day of CAP +1 to 238
9	7	40	EP	281	239-322
10	8	52	EP	minimum (last day of EP or 365)	323 to last day of EP

CAP: Controlled assessment period. EP: Extension period.

Table 3.2 Visit Windows: Fasting plasma glucose, Fasting Insulin, Plasma Exenatide

Visit	Analysis Visit	Week	Period	Target Day	Day range
2	0	0	CAP	1	Baseline
3	1	4	CAP	29	2-42
4	2	8	CAP	57	43-70
5	3	12	CAP	85	71-126
7	5	24	CAP	minimum (last day of CAP or 169)	127 to last day of CAP
10	8	52	EP	minimum (last day of EP or 365)	last day of CAP +1 to last day of EP

CAP: Controlled assessment period. EP: Extension period.

Table 3.3 Visit Windows: Fasting Lipids

Visit	Analysis Visit	Week	Period	Target Day	Day range
2	0	0	CAP	1	Baseline
5	3	12	CAP	85	2-126
7	5	24	CAP	minimum (last day of CAP or 169)	127 to last day of CAP

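### The windows in SAP Tables 3.8 and 3.9 open at Day 71, so in-period safety samples from Days 2 to 70 reach no by-visit table; the loss is clearest for calcitonin, amylase, lipase and CEA

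*SAP*

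**What the plan says.** SAP 4.3.3 assigns safety values to visits by study day.

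- **Table 3.8** (hematology, chemistry, urinalysis, growth and development hormones, bone markers) goes from baseline straight to Week 12, Days 71 to 126. Week 24 follows from Day 127.
- **Table 3.9** (calcitonin, pancreatic amylase, lipase, CEA) goes from baseline to a Week 12 window of "71 to last day of CAP", where CAP is the controlled assessment period. Its target day is "minimum (last day of CAP or 85". It has no Week 24 row.

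SAP 4.2.4.4 ties the laboratory tables to these windows: "observed values and changes from baseline to each post-baseline visit will be determined by visit windows described in Section 4.3.1 and 4.3.3". SAP 4.3.1 says visits follow the study day "rather than the nominal visit recorded in the eCRF", and that "the first step is to select all measurements falling within the study period". For a patient who does not enter the extension, the safety CAP ends at "date of last dose of randomized study medication + 7 days" (SAP 3.6.5.2).

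Early stoppers are meant to be sampled. SAP 3.6.3 invites them "for an ET visit to collect HbA1c, fasting plasma glucose, body weight, and clinical safety laboratory measures". Protocol 6.2.3.10, which covers Week 52 and Early Termination together, lists chemistry, hematology, calcitonin, "Pancreatic amylase and lipase", the hormones and CEA.

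**The concern.** A patient who stops in the first ten weeks can have a safety sample taken on schedule and within the defined safety period, and the SAP then gives that sample no visit. The instruction to map Early Termination data to the next scheduled visit appears in SAP 4.2.3.5, for secondary efficacy variables. Sections 4.2.4 and 4.3.3 have no counterpart for safety.

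Safety and tolerability over 24 weeks is a primary objective, and the protocol discusses pancreatitis and thyroid C-cell tumors among the risks (Section 1.3.1). For calcitonin, amylase, lipase and CEA the stated endpoint is change by visit (SAP 3.4 and 3.5). A patient missing from those tables may therefore have no summarized post-baseline value at all, although one was measured. The planned placebo arm is only 77 × 2/7 = 22 patients, so one or two absences would be visible.

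**Working it through.** The plan gives no figure to reproduce here. The check is of window coverage, followed by an illustrative count.

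**1. Day coverage up to Week 12.**

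| SAP table | Parameters | First windows after baseline | Days with no window |
|---|---|---|---|
| 3.3 | Fasting lipids | Week 12: 2–126 | none |
| 3.7 | Testosterone, SHBG, Tanner stage | Week 12: 2–126 | none |
| 3.5 | Vital signs | Week 4: 2–42; Week 8: 43–70; Week 12: 71–105 | none |
| 3.8 | Routine laboratory, hormones, bone markers | Week 12: 71–126 | 2–70, i.e. 70 − 2 + 1 = 69 days |
| 3.9 | Calcitonin, amylase, lipase, CEA | Week 12: 71 to end of CAP | 2–70, 69 days |

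Day 71 is the natural lower bound where Week 4 and Week 8 rows precede it, as in Table 3.5. It may have been carried into Tables 3.8 and 3.9 without those rows; that is an inference.

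**2. Who is affected.** Let L be the day of the last randomized dose. The safety CAP ends on L + 7. An early-termination sample on day d is assigned only if 71 ≤ d ≤ L + 7, which requires L ≥ 64. With nominal weekly dosing on Days 1, 8, 15 and so on:

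- L = 1 to 57: the CAP ends on Days 8 to 64. No in-period sample can be assigned, and the Table 3.9 range is empty because it would end before it starts.
- L = 64: the CAP ends on Day 71. Only a sample on Day 71 itself is assigned.
- L = 71: the CAP ends on Day 78. Every day from 72 to 78 is assigned, and the same holds for later stops.

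A sample taken after L + 7 is outside the safety CAP whatever the window.

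**3. Which outputs lose the value.**

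- Lost: observed and change-from-baseline tables by visit for all Table 3.8 and 3.9 parameters, and eGFR by visit, since eGFR comes from serum creatinine. For the eGFR model the effect is smaller. SAP Table 2 already excludes data after discontinuation of study drug, so the gap matters there only for samples taken up to that point.
- Kept: listings of chemistry, hematology, hormones and urinalysis, which include unscheduled samples. As worded, the shift to the minimum or maximum value during treatment is also kept for those groups.
- Unclear: SAP 4.3.4.1 mentions day windows in connection with shift analyses. The potential Hy's law table covers any time point but is laid out by visit.
- Not clearly covered elsewhere: calcitonin, amylase, lipase and CEA. The protocol's chemistry panel (6.4.5.1) omits them and 6.4.5.5 treats them as other evaluations. The SAP's listing and shift sentences do not name them.

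**4. Size (assumption).** Planned dropout is 10% of 77, or 7.7 patients. If it is spread evenly over 168 days, the share falling on Days 2 to 70 is 69/168 = 0.41, and 7.7 × 0.41 ≈ 3.2 patients. The count is zero if nobody stops early and about 8 if every planned dropout does. Each patient must also accept the invitation to the early-termination visit and be sampled by L + 7.

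**The case against.** The best defense is that no safety laboratory panel is scheduled between baseline and Week 12, and the endpoint is change to Week 12. A Day 10 value does not estimate that, so a window opening at Day 71 can be deliberate. This stands as an argument against relabelling early samples as Week 12. It does not justify giving them no place at all, and Tables 3.3 and 3.7 made the opposite choice on the same first visit.

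SAP 4.1.3.4 also says data beyond discontinuation are not analyzed. The reason it gives concerns the Extended Safety Follow-up Period; for safety data, 3.6.5.2 keeps seven days after the last dose.

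A reader might infer three stronger things that the documents do not support:

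- **That early stoppers vanish from safety reporting.** They do not. The listings, the min/max shifts as worded, the shift to the highest urinary albumin-creatinine category and the Hy's law outputs do not rest on a Week 12 label alone. Adverse events that led to study discontinuation are reported whatever their date (SAP 4.2.4.1).
- **That Table 3.9 routinely labels late early-termination values as Week 12.** SAP 4.3.4.1 takes the value closest to the target day, so a sample near Day 85 displaces one at Day 150. Mislabelling needs a patient with no sample near Day 85 and a later in-period sample.
- **That those lost mainly stopped for intolerance.** This is plausible, but neither document gives reasons or timing for early stopping.

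**Conclusion.** The gap is real and follows directly from the two tables: 69 study days belong to no visit, and nothing in the safety sections redirects the samples. Its reach is limited to by-visit observed and change tables and the eGFR analysis by visit. It weighs most for calcitonin, amylase, lipase and CEA, where by-visit change is the endpoint and no other summary is clearly assigned.

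The likely number is small: roughly 0 to 3 patients under even dropout, and at most about 8 if all planned dropout came before Day 71. Both figures rest on the protocol's 10% dropout assumption and on early-termination samples being taken within seven days of the last dose. The primary efficacy analysis is not affected. This is a worthwhile clarification, not a threat to the trial's conclusions.

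**What to change.** 1. For every Table 3.8 and 3.9 parameter, add a row for the last on-treatment value in the controlled period, taken from Day 2 to the last day of the CAP. It recovers every in-period sample without calling an early value Week 12.
2. State in SAP 4.2.4.4 that the min/max shift tables use all in-period values regardless of visit window, and that they include calcitonin, amylase, lipase and CEA.
3. Do not end the Table 3.9 Week 12 window at Day 126 on its own. Table 3.8 can stop there because its Week 24 row takes over at Day 127. Table 3.9 has no such row, so Days 127 to about 169 (43 days) would become a new gap. Shorten the window only together with the row in item 1, which keeps the later values.

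The cost is one extra row per table and two sentences of SAP text. No new data collection or hypothesis test is needed.
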